12.2.2 Contrast Agent Dose and Injection Rate

12.2.2.1 Feraheme® Dose and Injection Rate

Once patients are positioned and outfitted with receiver coils, venous access lines and physiological monitoring sensors, dilute Feraheme® will be administered by slow intravenous infusion to a total dose of 4 mg /kg (1,83). According to the recent FDA warning issued in March 2015, the entire therapeutic dose (510mg of Fe) of Feraheme should be injected as a slow infusion over 15 min or longer. For an average adult of 75kg body weight, 510 mg corresponds to 7 mg /kg and a 15 min infusion time corresponds to an infusion rate of 0.45 mg /kg.min. We will infuse 4 mg/kg of Feraheme which, at the rate suggested by the FDA, would require 8 min 30 sec to infuse. We will round this time up to 10 minutes for practicality and to ensure we do not exceed the recommended rate. The Feraheme will be diluted before injection for safety as well as practical reasons. The FDA warning dated March 2015 requires that Feraheme not to be injected without dilution to minimize risks of acute adverse reactions. The weight of patients in our study may range from 1kg (neonate) to 20 kg (6 year old). For neonates or small infants, the absolute volume of Feraheme to be used may be < 0.5 ml, and without significant dilution, controlling infusion of this volume over 10 minutes would be technically impractical. The factor by which the Feraheme can be safely diluted will also be influenced by the patient's physiological status. Patients with cardiac failure, a fixed cardiac output or with renal impairment may not tolerate a fluid challenge well.

For precise calibration of dose and delivery rate in the study group, the following considerations apply:

The stock formulation of Feraheme® is an isosmolar solution containing 30 mg elemental iron equivalent per ml. Therefore, 4 mg of iron is contained in 0.13 ml of undiluted Feraheme®. Total administered volume of undiluted Feraheme® is therefore 0.1333 ml /kg * weight in kg. Due to the requirement to infuse over several minutes, the stock formulation will be diluted by a factor of 6-30 with normal saline and infused over 10 minutes (600 secs). This rate corresponds to an 18 minute infusion period for a 500 mg dose of iron in a 70 kg adult and is therefore within the 15 minute infusion guideline set forth by the FDA in March, 2015.

12.2.2.2 Ablavar Dose and Injection Rate

Each patient in the Ablavar group of our study will receive 0.03 mmol/kg of Ablavar, the FDA approved dose for MR angiography. The Ablavar will be diluted up to 8 fold and injected over 15-20 seconds (86). These dose and injection rates are consistent with our current institutional standard practice.

12.2.3 MRI Scanning Procedures

As for all patients, the MRI system will perform automatic adjustment procedures to optimize the homogeneity of the magnetic field, customized to the individual patient. It will also perform standard RF frequency adjustment of the transmitter RF field and calibration of the receiver coil elements. All parameters for RF dose (SAR or specific absorption rate) and gradient switching rates will be within FDA approved limits and monitored continuously by permanent and immutable software and hardware watchdogs (Siemens product specifications on file at FDA).

With the patient being ventilated continuously, the following MRI pulse sequences will be performed:

For Study Part I, each patient (regardless of test or control group assignment) will undergo MRI using the following MRI pulse sequences: 1) Conventional 2D cine imaging for cardiac function assessment and phase-contrast MRI for flow quantification in imaging planes specified by a radiologist or cardiologist at the point of delivery, per our institutional standard practice regardless of our research protocol. These image acquisitions are necessary to ensure that each patient will get a diagnostic MRI study regardless the outcome of our research and will only be performed when the patient is considered by the supervising anesthesiologist to be stable for ventilator-controlled breath-hold maneuvers; 2) The 3D cine ventilator-gated MUSIC-MRI MRI, based on which the Feraheme vs. Ablavar comparison will be performed.

For Study Part II, each patient will undergo the same MRI pulse sequence as Part I of our study. In addition, each patient will undergo the to-be-developed self-gated MUSIC-MRI MRI and the order of the ventilator-gated MUSIC-MRI and the self-gated MUSIC-MRI will be randomized. The self-gated MUSIC-MRI pulse sequence will require an additional 5 min of scan time and anesthesia time without breath holding, which the investigators feel does not add significant additional risk to the patient.

13 EVALUATIONS BY VISIT (ONLY 1 VISIT)

13.1 Visit 1 (Day/Week/Month #)

1. Clinical indication for contrast enhanced cardiovascular MRI established by discussion involving the referring clinician and the Investigators or designee.
2. Clinical rationale for Feraheme vs. Ablavar is discussed with the patient's legal guardian(s) by the Investigators or designee in Part I of the study and the patient's legal guardian(s) are given the choice to choose Feraheme vs. Ablavar as the contrast agent. In Part II of the study, the superior contrast agent as determined in Part I of the study will be used and the benefits and risks of undergoing a combination of ventilator-gated MUSIC-MRI and self-gated MUSIC-MRI will be discussed with the patient's legal guardian(s)
3. Obtain written informed consent and HIPAA authorization and assent, if appropriate by the Investigators or designee.
4. Assign the subject a unique screening number.
5. Record demographics data.
6. Record medical history, including a history of hypersensitivity reactions to iron products and iron overload. Screen for inclusion and exclusion criteria.
7. Procedure for sedation and cardio-respiratory support discussed with the anesthesiologist or NICU staff by the Investigator or designee.
8. Patient undergoes general anesthesia with endotracheal intubation or is transported sedated and intubated from the NICU.
9. Record concomitant medications.
10. Perform and record vital signs.
11. Perform and record oximetry.
12. Perform and record results of blood pressure testing.
13. Contrast infusion.
14. Continue monitoring and recording vital signs and oximetry up to 30 min after infusion
15. MRI exam (ventilator-gated MUSIC-MRI for Part I of the study, and both ventilator-gated and self-gated MUSIC-MRI for Part II of the study).
16. Patient recovers from anesthesia/sedation.

It is noted that one or more of Items 1-through-7 may occur on a day different from (prior to) the day of the MRI study. All of these procedures will be included in 'Visit 1' with relevant dates as appropriate.

14 ADVERSE EXPERIENCE REPORTING AND DOCUMENTATION

14.1 Adverse Events

An adverse event (AE) is any untoward medical occurrence in a clinical investigation of a patient administered a pharmaceutical product and that does not necessarily have a causal relationship with the treatment. An AE is therefore any unfavorable and unintended sign (including an

abnormal laboratory finding), symptom or disease temporally associated with the administration of an investigational product, whether or not related to that investigational product.

The Investigator will probe, via discussion with the subject, for the occurrence of AEs during each subject visit and record the information in the site's source documents. Adverse events will be recorded in the patient CRF. Adverse events will be described by duration (start and stop dates and times), severity, outcome, treatment and relation to study drug, or if unrelated, the cause.

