
Table 5: A comparison of AE/SAE incidence rates for Feraheme vs. Ablavar based on FDA/EMA product labels.

AE Type	Feraheme	Ablavar
Hypersensitivity/anaphylactic	0.1%-0.2%	0.1%-0.2%
Risks of NSF for patients with renal impairment?	No	Yes
Risks of arrhythmia due to prolongation of ECG QT interval	No	Yes

Pruritus	1.2%	4%
Hypertension	1.0%	1%
Dizziness	2.6%	1%
Headache	1.8%	4%
Nausea	3.1%	4%
Hypotension	2.5%	(<1% and not shown on the Prescribing Information)
Edema	1.5%	
Vomiting	1.5%	
Abdominal pain	1.3%	
Chest pain	1.3%	
Cough	1.3%	
Pyrexia	1.0%	
Back pain	1.0%	
Muscle spasms	1.0%	
Dyspnea	1.0%	
Rash	1.0%	(<1% and not shown on the Prescribing Information)
Vasodilatation		
Paresthesia		
Injection site bruising		
Dysgeusia		
Burning sensation		
Venipuncture site bruise		
Feeling cold		1%

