9.2 Inclusion Criteria

1. Male or female pediatric patients (age newborn to 6 years) of all ethnicities with known or suspected CHD with insufficient echocardiographic exams and are referred for cardiovascular MRI for further evaluation of cardiac anatomy and function.
2. Written informed consent obtained from subject's legal representative/guardian(s) and ability for subject to comply with the requirements of the study.

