12.1 Clinical Assessments

Concomitant Medications

All concomitant medication and concurrent therapies will be documented at the date of study MRI. Dose, route, unit frequency of administration, and indication for administration and dates of medication will be captured.

Demographics

Demographic information (date of birth, gender, race) will be recorded at Screening.

Medical History

Relevant medical history, including history of current disease, other pertinent respiratory history, and information regarding underlying diseases will be recorded at Screening.

Physical Examination

N/A

Vital Signs / Oximetry / Ventilatory Parameters

Continuous heart rate, blood pressure, ECG, pulse oximetry, and end tidal CO_2 will be monitored for the duration of the MRI study and until the subject is recovered or returned to the Intensive Care facility, or for 30 minutes after the infusion, whichever is longer.

Adverse Events

Information regarding occurrence of acute adverse events will be captured throughout the study. Duration (start and stop dates and times), severity/grade, outcome, treatment and relation to study drug will be recorded on the case report form (CRF). Each patient will be followed up via a review of medical record at 60 days after MRI study to capture any additional AEs.

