12.2 MRI Procedures

12.2.1 Patient Preparation and Setup

All patients will undergo MRI on an FDA approved, clinical 18-channel Siemens 3.0T Magnetom TIM Trio scanner, and running version B17 software. The appropriate RF receiver coil configuration will be chosen depending on patient size; for example neonates may be studied using a 16 element adult knee coil, infants using an adult head-neck coil combination and older children using surface flex coils or a body array coil. Fixed (spine) coil elements in the patient table may be used in combination with any of the other coils (except the knee coil).

Prior to Feraheme or Ablavar infusion, all patients will be asleep, intubated and ventilated such that, in the case of a clinically urgent or life-threatening AE, there will already be in place full

airway protection, physiological monitoring and support of respiration. Consistent with institutional clinical practice at UCLA, anesthesia in the pediatric CHD patients will be performed by specialized pediatric anesthesiologists regardless of contrast agent used (Feraheme vs. Ablavar) with continuous monitoring of heart rate, blood pressure, pulse oximetry, end tidal CO₂, and, where appropriate, anesthetic gas levels (such as sevoflurane). In the case of a SAE, changes in vital signs will be recognized immediately and appropriate treatment initiated. All of the children in our study will have protected airways and mechanical ventilatory support from the start of the procedure to the end. Serious adverse reactions to any agent may include laryngeal edema and bronchospasm, where prior endotracheal intubation may be lifesaving. Should other events occur involving changes in heart rate, heart rhythm and /or blood pressure, the anesthesiologist can focus his / her attention on the appropriate use of chronotropic or inotropic agents, intravenous fluids and /or vasoactive drugs, without having to secure the airway. All patient physiological monitoring data are, and will continue to be, digitized and transferred in real time to the electronic patient medical record, where they are stored permanently and retrievably. Relevant abstractions from these and other patient safety data (protected health information removed) will be included in our DMC, IRB and IND adverse event reports.

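### After recovery from anesthesia an adverse event is counted only if it reaches a medical record, because section 14.1 relies on talking to the child and no visible section has the guardian asked after dosing

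*Combined protocol and SAP*

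**What the plan says.** The elicitation rule is in section 14.1: "The Investigator will probe, via discussion with the subject, for the occurrence of AEs during each subject visit". Four other places determine how it works in practice.

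- **Who the subject is.** Section 9.2 admits "Male or female pediatric patients (age newborn to 6 years) of all ethnicities".
- **State at dosing.** Section 12.2.1: "Prior to Feraheme or Ablavar infusion, all patients will be asleep, intubated and ventilated".
- **Number of visits.** Section 13 is a single-visit schedule ("EVALUATIONS BY VISIT (ONLY 1 VISIT"). Its 16 steps include no AE enquiry of the child, the guardian or a nurse. The last step is "Patient recovers from anesthesia/sedation".
- **What follows the visit.** Section 12.1: "Each patient will be followed up via a review of medical record at 60 days after MRI study to capture any additional AEs". The synopsis describes the same 60-day record review.

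Section 12.1 also requires acute AEs to be captured on the case report form throughout the study, and vital signs to be monitored "until the subject is recovered or returned to the Intensive Care facility, or for 30 minutes after the infusion, whichever is longer". Section 14.2 stops collecting serious AEs (SAEs) once the procedures of the study visit are done. AE incidence is a named safety endpoint in 8.1.3 and 8.2.3, and section 18.6 analyses it descriptively.

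**The concern.** The one sentence that says how AEs are to be asked about names an informant who, for most of this population, cannot answer. A newborn or toddler cannot report symptoms. An older child can do so only after waking, at the very end of the only visit. The guardian, who would normally answer for the child, is interviewed before the study (section 5.2), and no visible section has the guardian asked again after contrast.

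What is at stake is the third study objective, to summarize the safety of both agents. If delayed mild events are seen only when charted, a low recorded rate mixes a low true rate with limited observation, and the report cannot separate the two. Charting also depends on where the child is. A child who stays in intensive care is recorded continually, whereas a child who goes home is recorded only on returning. Section 18.6 pools Parts I and II by agent, and exclusion criterion 5 (critically ill children) applies to Part II only. The mix of inpatients and outpatients behind each agent's pooled rate could therefore differ.

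**Working it through.** The plan gives no figure for AE capture, so there is nothing to reproduce. The check sets the capture routes side by side.

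1. **Contrast to recovery.** Source: continuous monitoring and case report form capture (12.1), by anesthesia or intensive care staff. Acute hemodynamic, respiratory and visible events are covered, including those seen as the child wakes. No gap is claimed here.
2. **Discussion with the subject (14.1).** Window: the single visit. For most children aged 0 to 6 this yields little or nothing, and 13.1 does not schedule it.
3. **After recovery to day 60.** Source: the medical record review only (12.1, synopsis). It sees an event if, and only if, the event was charted. The documents do not say whether records outside the site are read.
4. **SAEs after the visit.** Section 14.2 has closed collection, while 12.1 is still looking for additional AEs at day 60. The two windows do not match.

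Table 6 shows which events fall through route 3. Its mildest grade is defined by needing no medical treatment, and in a child already at home such an event will seldom produce a chart entry.

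**Scale only.** Let *n* be the children in a group, *p* the true rate of an event and *c* the fraction of events captured. The expected recorded count is *n·p·c*, and the chance of recording at least one is 1 − (1 − *p·c*)^*n*. Inputs: *n* = 40 (section 18.7.1) and *p* = 1.5% (vomiting, Feraheme, Table 5, assumed to apply here). The values of *c* are assumptions, because the documents give none.

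- *c* = 1: 1 − 0.985^40 = 45%; expected count 0.60
- *c* = 0.5: 1 − 0.9925^40 = 26%; expected count 0.30
- *c* = 0.25: 1 − 0.99625^40 = 14%; expected count 0.15

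If 0 of 40 are recorded, the one-sided 95% upper limit for the recorded rate is 1 − 0.05^(1/40) = 7.2%. As a limit for the true rate this becomes 7.2% / *c*, which is about 14% at *c* = 0.5. These figures show how incomplete capture weakens a reassuring zero. They do not estimate the loss in this trial.

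**The case against.** The strongest reply is that the plan does capture AEs by other means, and much of that reply stands. Monitoring runs through recovery, 12.1 independently requires AE recording with severity, outcome and relatedness, and the 60-day review counts every charted reaction. The AEs of special interest in 18.6, hypersensitivity and blood pressure changes requiring intervention, are the kind that monitoring targets. A reader might infer that all reactions after recovery go uncounted. The documents do not support that; only uncharted events are at risk.

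A reader might also add up the symptom rates in Table 5 and take the total as the number of events lost per group. That fails for four reasons. The rates come from labels for agents approved in adults, and section 4.7.3 gives the Feraheme rates for the full therapeutic dose, whereas the study dose is described as about half of that. Events may overlap. Several of the symptoms, such as headache or dizziness, are ones an infant could not convey to a guardian either. The sum would also assume near-zero capture. The protocol's own imaging data point lower. Leaving out the study with no AE rate reported, Table 3 shows 4 + 1 + 1 = 6 AEs in 198 to 215 patients (one study gives both 68 and 85 as its number), or about 3%, roughly 1.2 per 40. Those reports may under-ascertain too.

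Third, a reader might conclude that the choice of agent for Part II is compromised. Section 7.3 brings safety into that choice only if Part I is not significant, as the third of three factors, and its examples are severe or long-term risks. Nor does any section show that inpatient share differs by agent, so differential capture is a possibility and no more.

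Finally, the text of section 14.3 (Medical Monitoring) and the consent form were not available for this check. A reporting instruction to guardians could be there.

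**Conclusion.** The point holds in a limited form. The informant named in 14.1 does not fit the population, no visible section has the guardian asked after dosing, and from recovery to day 60 an AE counts only if it was charted. Mild or home-treated delayed events are therefore likely to be undercounted in a named safety endpoint, possibly unevenly between inpatients and outpatients. The size cannot be derived from the documents, because they give neither a capture fraction nor an event rate for children at this dose. The conclusion assumes that mild events in discharged children are seldom charted and that the unavailable pages contain no guardian reporting instruction. No efficacy result, sample size or formal test is affected. This is an inexpensive improvement that should be made, and it is not a defect that undermines the trial.

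**What to change.** - In 14.1, name the legal guardian as informant, or bedside staff for inpatients, together with the child where old enough.
- In 13.1, add a short standard AE query after recovery and before discharge or transfer.
- Add one guardian contact after discharge, alongside the 60-day review, with the same questions in both agent groups.
- State whose medical records the 60-day review covers: the site's only, or outside care as well.
- In 18.6, report AE incidence by source (monitored, asked, charted), so that a reader can see how each event was found.
- Reconcile the SAE collection window in 14.2 with the 60-day AE follow-up in 12.1.

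The cost is wording in the protocol and case report form and, as an estimate, a few minutes of staff time per child across 120 children. Reported AE rates will look slightly less favourable, because more events will be found. For events that neither a guardian nor a nurse can observe in an infant, the query will recover little.

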14.1.1 AE Severity

The National Cancer Institute's Common Terminology Criteria for Adverse Events (CTCAE) Version 4.0 should be used to assess and grade AE severity, including laboratory abnormalities judged to be clinically significant. If the experience is not covered in the criteria, the guidelines shown in Table 6 below should be used to grade severity. It should be pointed out that the term "severe" is a measure of intensity and that a severe AE is not necessarily serious.

Table 6. AE Severity Grading

Severity (Toxicity Grade)	Description
Mild (1)	Transient or mild discomfort; no limitation in activity; no medical intervention or therapy required. The subject may be aware of the sign or symptom but tolerates it reasonably well.
Moderate (2)	Mild to moderate limitation in activity, no or minimal medical intervention/therapy required.
Severe (3)	Marked limitation in activity, medical intervention/therapy required, hospitalizations possible.
Life-threatening (4)	The subject is at risk of death due to the adverse experience as it occurred. This does not refer to an experience that hypothetically might have caused death if it were more severe.

14.1.2 AE Relationship to Study Drug

The relationship of an AE to the study drug should be assessed using the following the guidelines in Table 7.

Table 7. AE Relationship to Study Drug

Relationship to Drug	Comment
Definitely	Previously known toxicity of agent; or an event that follows a reasonable temporal sequence from administration of the drug; that follows a known or expected response pattern to the suspected drug; that is confirmed by stopping or reducing the dosage of the drug; and that is not explained by any other reasonable hypothesis.
Probably	An event that follows a reasonable temporal sequence from administration of the drug; that follows a known or expected response pattern to the suspected drug; that is confirmed by stopping or reducing the dosage of the drug; and that is unlikely to be explained by the known characteristics of the subject's clinical state or by other interventions.

Possibly	An event that follows a reasonable temporal sequence from administration of the drug; that follows a known or expected response pattern to that suspected drug; but that could readily have been produced by a number of other factors.
Unrelated	An event that can be determined with certainty to have no relationship to the study drug.

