18.6 Safety Evaluations

AEs, SAEs, AEs resulting in premature withdrawal from the study, AEs of special interest (hypersensitivity reactions and blood pressure changes requiring intervention), and study related adverse events will be listed and summarized by contrast agent group. For the purpose of safety evaluation, the patients in both Part I and Part II who received the same contrast agent will be included in a single safety report. Due to the limited study cohort size and the small anticipated AE rates, no formal inferential statistical analyses will be performed for AEs. However, while the study is too small to expect statistical significance in sub-groups, the efficacy and safety results will be examined by standard age categories (neonates (0-to-1 month of age), infants and toddlers (1 month to 2 years of age) and children (>2 years of age)) and any clinically important differences reported.

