20 ADMINISTRATIVE, ETHICAL, REGULATORY CONSIDERATIONS

The study will be conducted according to the Declaration of Helsinki, Protection of Human Volunteers (21 CFR 50), Institutional Review Boards (21 CFR 56), and Obligations of Clinical Investigators (21 CFR 312).

Any serious, unexpected suspected adverse reactions, findings from other clinical, animal, or in-vitro studies that suggest significant human risk, and any clinically important increases in the rate of a serious suspected adverse reaction will be sent to the FDA, Division of Medical Imaging Products, and to all investigators no later than 15 calendar days after determining that the information qualifies for reporting [21 CFR 312.32(c)(1)]. Additionally, any unexpected fatal or life-threatening suspected adverse reaction will be reported to the FDA Division of Medical Imaging Products no later than 7 calendar days after initial receipt of the information [21 CFR 312.32(c)(2)]. Each submission will be addressed to the Regulatory Project Manager and/or the Chief, Project Management Staff for the Division.

To maintain confidentiality, all reports, evaluation forms, and other records will be identified by a coded number and initials only. All study records will be kept in a locked file cabinet and code sheets linking a patient's name to a patient identification number will be stored separately in

another locked file cabinet. Clinical information will not be released without written permission of the subject, except as necessary for monitoring by the FDA. The Investigator must also comply with all applicable privacy regulations (e.g., Health Insurance Portability and Accountability Act of 1996, EU Data Protection Directive 95/46/EC).

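### Table 7 builds expectedness into every related causality grade, so an unfamiliar reaction has no grade and events known for only one agent can be graded differently

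*Combined protocol and SAP*

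**What the plan says.** Table 7 in section 14.1.2 offers four grades of relationship to study drug.

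- **Definitely** begins "Previously known toxicity of agent; or an event that follows a reasonable temporal sequence from administration of the drug". The text after the 'or' continues "that follows a known or expected response pattern to the suspected drug; that is confirmed by stopping or reducing the dosage of the drug", and finally asks that no other reasonable hypothesis explain the event.
- **Probably** repeats the timing, pattern and dechallenge conditions, with other explanations unlikely.
- **Possibly** asks for reasonable timing and an event "that follows a known or expected response pattern to that suspected drug; but that could readily have been produced by a number of other factors".
- The fourth grade, **Unrelated**, is "An event that can be determined with certainty to have no relationship to the study drug".

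There is no unlikely, unknown or residual grade.

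Two other sections rely on the idea of relatedness. Section 18.6 says that "study related adverse events will be listed and summarized by contrast agent group". Section 20 sets expedited timelines for "Any serious, unexpected suspected adverse reactions", among other findings. Table 5 in section 4.7.3 gives the two agents partly different known profiles.

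**The concern.** Whether an event is already known for a drug, and whether the drug caused this particular event, are separate questions. Table 7 answers the second largely through the first. Two consequences follow.

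First, a reaction of a new kind cannot be placed. Both agents are described as approved in adults (sections 4.3, 4.6 and 11.3), and this trial enrols newborns to 6-year-olds with congenital heart disease. Unfamiliar reactions are among those a safety review should be able to record as suspected.

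Second, the grade of a given event can depend on which agent's label mentions it. All children are anaesthetised and ventilated (section 12.2.1), and records are reviewed for further events at 60 days (section 12.1), so events with other causes are plausible in both groups. The investigators know the agent (Synopsis, Planned Interim Analyses).

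The by-agent summary of related events could then differ for reasons of labelling. If Part I is not significant, section 7.3 asks the DMC to weigh safety differences seen in Part I when advising on the Part II agent, so that summary could inform the advice.

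**Working it through.** No sample size, power or alpha figure is involved, so there is no plan figure to reproduce. The check treats Table 7 as a decision rule.

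Conditions, all from Table 7:

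- K: previously known toxicity of the agent
- T: reasonable timing
- P: known or expected pattern
- D: confirmed by stopping or reducing the drug
- E: no other reasonable explanation
- U: other explanations unlikely
- A: other factors could readily have produced the event
- N: certainty of no relationship

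The rule on its plain reading:

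- Definitely = K or (T and P and D and E)
- Probably = T and P and D and U
- Possibly = T and P and A
- Unrelated = N

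**Case 1, new kind of reaction** (T true; K and P false). Definitely, Probably and Possibly all fail. Unrelated fails unless N holds. The event has no grade.

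**Case 2, QT-related arrhythmia with other plausible causes** (T and A true; D false). Table 5 marks this risk as Yes for Ablavar and No for Feraheme.

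- After Ablavar, K and P are true. The event is Definitely by the first clause. It also satisfies Possibly, and the table has no rule for choosing between them.
- After Feraheme, K and P are false and no related grade applies.

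**Case 3, hypotension with other plausible causes** (T and A true; D false). Table 5 gives 2.5% for Feraheme; the Ablavar entry is "<1% and not shown on the Prescribing Information".

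- After Feraheme, K is true and the event is Definitely.
- After Ablavar, the result turns on whether an unlisted event below 1% counts as known. If not, no related grade applies; if so, it is Definitely. Table 7 leaves this to the assessor.

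Cases 2 and 3 push in opposite directions.

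**Case 4, nausea.** Table 5 gives 3.1% for Feraheme and 4% for Ablavar. K is true for both, so the grade is the same. This also holds for hypersensitivity or anaphylaxis, pruritus, hypertension, dizziness and headache.

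**Alternative reading.** The semicolons in Definitely could mean that the later conditions also govern known toxicity, so that K no longer suffices alone. Case 1 still has no grade. In case 2 the Ablavar event becomes Possibly and the Feraheme event still has no related grade. Both consequences survive, with a smaller gap between the grades.

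**Set beside section 20.** That section presupposes a reaction that is both unexpected and suspected. Every related grade in Table 7 requires a known toxicity or a known or expected pattern, so the table has no related grade for such a reaction.

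**The case against.** The case for leaving the table alone has substance.

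- **Known toxicity is not the only test.** It is one of two routes into one of four grades. The gap for new reactions comes from the pattern condition, not from the opening clause. This stands. A reader might infer that identical events are graded differently by agent in general. Table 5 does not support that: case 4 shows that events listed for both agents get the same result by this route.
- **Timing is not wholly absent.** Section 14.1 defines an adverse event as temporally associated with administration, so a loose timing condition applies before Table 7 is used. Table 7 is also introduced as guidance. Both stand, but neither supplies the missing consideration of other causes.
- **Safety reporting does not pass through Table 7.** A reader might infer that expedited reports would be blocked. The documents do not say so. Section 20 applies the federal regulation directly and does not cite the table. Section 14.2 documents serious events irrespective of relatedness, and section 20.2 sends them to the IRB on the same basis. Section 18.6 summarises all events, serious events and events of special interest (hypersensitivity, and blood pressure changes needing intervention) separately from related ones. This stands and limits the reach of the point.
- **A large imbalance cannot be shown.** A reader might put a count on it: if 30% of 40 children per group had a Feraheme-listed event from other causes, 0.30 × 40 = 12 would be Definitely with Feraheme and about 0 with Ablavar. The documents give no such rate. Their institutional data report no adverse events in 79 children (section 4.7.2) and none in 35 monitored for up to 1 hour (Table 4), which says nothing about 60 days. The zero for Ablavar treats rare and unlisted as unknown, and in the text available the Ablavar cells for vomiting, cough and pyrexia are blank. Choosing only Feraheme-listed events also leaves out the QT example, which runs the other way.

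**Conclusion.** The point holds as a defect in a stated rule. Table 7 mixes expectedness with causality, leaves a plausibly timed but unfamiliar event without a grade, and can grade the same clinical picture differently where the agents' known status differs. The direction can favour either agent, and no numerical size can be given from the documents.

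The exposed output is one descriptive table, the by-agent summary of study-related events, with a possible onward effect on the DMC's advice about Part II. No inferential test or decision rule uses the causality grade. The change should be made, but the point does not threaten the primary analysis or the reporting of serious events.

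The conclusion assumes that investigators apply Table 7 as written and take known status from sources such as Table 5. The text of section 14.3 (Medical Monitoring) was not available; I assume that it does not redefine the grades.

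**What to change.** In Table 7:

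1. Delete the opening known-toxicity clause of Definitely and the 'or' that follows it.
2. Make a known or expected pattern supportive rather than required, so that an event with plausible timing and no clearly more likely cause is at least Possibly.
3. Replace certainty in Unrelated with a residual definition (no plausible timing, or clearly better explained by another cause), or add an Unlikely grade, so that every event has a grade.
4. Record expectedness in a separate case report form field, for use with section 20.

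Step 3 is needed because of step 1. Take a fever on day 45 after Feraheme, which Table 5 lists as pyrexia at 1.0%. It is Definitely today through the known-toxicity clause. With that clause gone and Unrelated still at certainty, it would lack plausible timing for any related grade and would have no grade at all.

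The dechallenge condition in Definitely and Probably is a separate matter. It can hardly be shown for an injection of 15-20 seconds (section 12.2.2.2), and it is sensible to review it in the same edit.

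The cost is rewording one table and adding one case report form field, with some more events graded Possibly. No dose, procedure, sample size or clinical rule changes.
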